Title: No Post Intubation Laryngeal Symptoms (No-PILS)

NCT05383417

Date: April 12, 2023

Study Protocol

Description:

Single center randomized controlled trial with 100 subjects who will be intubated for already planned surgeries. The participants will be randomized into the control group or the clip group. The clip group will have a small clip (the endotracheal tube support device, also known as EndoClip) placed on the endotracheal tube to reduce the pressure on the vocal cords and larynx. This endotracheal tube support device is made from a FDA approved biocompatible material. The University of California San Diego Institutional Review Board ("IRB") approved this study (IRB #800842).

The control group subjects will undergo their planned procedure with no intervention during intubation. The clip group will undergo their planned procedure as normal but with the EndoClip placed on the endotracheal tube by the assigned anesthesia attending physician or trained clinician. The EndoClip is placed once the tube is secured and the ventilator circuit is connected. While extubating the patient, the endotracheal tube will be removed with the EndoClip attached and a picture of the tube will be taken to record the clip location.

Before the planned procedure, the investigators will survey the participants to get a baseline for any pre-existing laryngeal symptoms. The same survey will be administered after the procedure when the participants are awake and alert ('Day 0'), 24 hours ('Day 1'), 48 hours ('Day 2'), and 1 week ('Day 7') after the procedure. The survey will ask the participant to indicate "yes" or "no" for whether they are experiencing a sore throat, throat pain, oral pain, difficulty speaking, difficulty swallowing, changes in their voice, pain while speaking, and pain while swallowing. If they have indicated "yes" for any of the symptoms, the participants will also be asked to rate the severity on scale from 0 (no pain/difficulty) to 10 (severe pain/difficulty). If they indicate "no", this will be considered a score of 0 for the respective outcome variable.

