Other data points will also be collected in this study that are related to the intubation and participant's airway. The investigators will record the total time of the procedure and the length of time the clip is placed on the endotracheal tube. For each participant in the clip group, the investigators will also record the time it takes to place the clip on the endotracheal tube. Each participant's airway will be evaluated, and the investigators will record the thyromental distance, Mallampati score, history of difficult intubation, and the size of the endotracheal tube used. Lastly, data from each participant's intubation will be collected including number of attempts before successful intubation, incidence of dental injury, incidence of lip injury, laryngeal view on Cormack-Lehane scale, and any noted trauma upon extubation.

At any point during the study, the participant can withdraw from the study. All study participants will be identified according to a number assigned at the beginning of the study, using key code.

Study Design:

Study Type:	Interventional
Primary Purpose:	Prevention
Study Phase:	Closed
Interventional Study Model:	Parallel Assignment

	2 arm parallel trial where one group will receive the endotracheal tube clip (EndoClip) during general endotracheal anesthesia and the other group will not (control)
Number of Arms:	2
Masking:	Double (Participant, Outcomes Assessor) Patient will not be aware of their treatment arm. Investigator and Care Provider will be aware of treatment arm but data analysis (outcomes assessor) will be blinded to treatment groups.
Allocation:	Randomized
Enrollment:	100 [Actual]

Arms and Interventions:

Arms	Assigned Interventions
Experimental: EndoClip Clip applied to endotracheal tube.	Device: EndoClip Clip attached to mid portion of the endotracheal tube. Other Names: 
• Endotracheal tube clip• Endotracheal tube support clop• Endotracheal tube support device
No Intervention: No Clip No clip applied to endotracheal tube.	

Outcome Measures:

Primary Outcome Measure:

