AH2) Reducing the force on the vocal cords will change the duration of laryngeal symptoms in participants who underwent Endotracheal Intubation

We will use IBM SPSS Statistics, version 28.0.1.1 (14). Student's t-test will be used to compare symptom severity at each time point while Pearson's chi-square test will be used to compare the incidence of throat symptoms across groups. Multiple regression analysis will be used to evaluate demographic and anesthesia variables as predictors of throat symptoms. The odds ratio (OR) and their 95% confidence interval (CI) will be reported for each covariate included in the model. The level of significance (p) to be considered is 0.05.

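### The only multivariable model promises odds ratios but names neither treatment arm nor the baseline symptom, so no adjusted clip effect is planned, and its covariate set is left open at N = 100

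*Combined protocol and SAP*

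**What the plan says.** The Statistical Analysis Plan gives two sentences to modelling: "Multiple regression analysis will be used to evaluate demographic and anesthesia variables as predictors of throat symptoms" and "The odds ratio (OR) and their 95% confidence interval (CI) will be reported for each covariate included in the model". It does not say whether the regression is linear, logistic or ordinal, which symptom and time point it concerns, or whether the dependent variable is the yes/no item or the 0-10 score. It gives no covariate list or selection rule. On testing it adds only: "The level of significance (p) to be considered is 0.05".

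The arms are compared separately and without adjustment: "Student's t-test will be used to compare symptom severity at each time point while Pearson's chi-square test will be used to compare the incidence".

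The Description sets the size: "Single center randomized controlled trial with 100 subjects who will be intubated for already planned surgeries". Each symptom has a yes/no answer and a severity score, linked by the rule "If they indicate 'no', this will be considered a score of 0 for the respective outcome variable". The same survey is given before the procedure, so a baseline value is collected. Under Eligibility, only severe pre-existing sore throat, voice change or swallowing trouble is excluded.

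The Description also lists data to be collected: "the investigators will record the thyromental distance, Mallampati score, history of difficult intubation, and the size of the endotracheal tube used". To these it adds procedure time, clip duration and placement time, intubation attempts, dental and lip injury, laryngeal view and trauma at extubation. It does not say which of these enter the regression.

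**The concern.** The trial asks whether the clip changes symptoms. Its one multivariable model is described only as a search for predictors, with neither the randomised arm nor the pre-procedure symptom named. Patients with mild symptoms at baseline can enrol, so the baseline value is an obvious candidate for adjustment. As written, that information is collected but has no stated place in the estimate of the clip effect.

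Two further matters follow from the brevity of the text. The name of the method and the promised effect measure fit together only if a particular model is assumed. The open covariate set would also permit a model too large for 100 patients. In that case published predictor ORs could be too far from 1, or not estimable, and no plan would exist against which to check them.

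**Working it through.** The plan gives no event rate, covariate count or power figure, so it has no figure to reproduce. Only N = 100 and the 0.05 level come from the documents. Incidences, model sizes, equal allocation and prevalences below are assumptions.

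**1. Method against output.** Suppose incidences of 40% and 20%. A linear model of the yes/no item gives a coefficient of 0.20 − 0.40 = −0.20, a risk difference. The OR is (0.20/0.80)/(0.40/0.60) = 0.375. A linear model of the 0-10 score gives a mean difference. Only a logistic or ordinal logistic model gives the promised OR.

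**2. How open the outcome is.** Six primary symptoms at four post-procedure times give 6 × 4 = 24 possible yes/no outcomes.

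**3. Size of a model that used everything.** Ten collected variables have meaning in both arms: procedure time, thyromental distance, Mallampati, difficult-intubation history, tube size, attempts, dental injury, lip injury, laryngeal view and extubation trauma. They take 10 degrees of freedom, or 14 if Mallampati and laryngeal view are 4-level factors (8 + 3 + 3). Age, sex and arm bring this to 13 to 17. Events per term = 100 × incidence / terms:

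| Incidence | 13 terms | 17 terms | 3 terms |
|---|---|---|---|
| 10% | 0.77 | 0.59 | 3.3 |
| 20% | 1.54 | 1.18 | 6.7 |
| 40% | 3.08 | 2.35 | 13.3 |
| 50% | 3.85 | 2.94 | 16.7 |

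**4. Effect on the ORs.** Maximum-likelihood logistic fits were simulated with n = 100, 50 per arm, arm always in the model, a true OR of 2.0 for one binary covariate and 2,000 replicates per scenario. Columns 2 to 4 give the geometric-mean OR among fits that converged. The last column gives the share of fits that failed or had a non-finite coefficient when four rare binary items (prevalence 1%, 3%, 3% and 5%) were included.

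| Incidence | 3 terms | 9 terms | 17 terms | 13 terms with rare items: failed |
|---|---|---|---|---|
| about 11% | 2.10 | 2.40 | 3.14 | 98% |
| about 21% | 2.13 | 2.33 | 2.56 | 93% |
| about 40% | 2.08 | 2.18 | 2.39 | 83% |
| about 50% | 2.05 | 2.21 | 2.36 | 80% |

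With 17 terms the OR is 18% (2.36/2.0) to 57% (3.14/2.0) too large. With 3 terms it is about 2% to 7% too large. The failures depend on the assumed rarity: at 1% prevalence about one patient in 100 has the item, and a single carrier gives an infinite coefficient. Without rare items, 3.7% of 3-term fits and 11.7% of 17-term fits fail at about 11% incidence.

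**5. A second set of assumptions.** With arm plus 12 standard-normal covariates, a true log-OR of 0.50 and baseline event rates of 10% to 40%, the mean estimate is 0.61 to 0.71. On the OR scale that is exp(0.61) = 1.84 to exp(0.71) = 2.03 against exp(0.50) = 1.65, or 12% to 23% too large. With 3 covariates it is 0.53 to 0.56, or about 3% to 6% too large.

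**6. False predictors.** In that 12-covariate setting, at least one of 11 null covariates reaches p < 0.05 in 44% to 49% of trials. Independent tests alone would give 1 − 0.95^11 = 43%, so nearly all of this is the number of tests. With two null covariates the figure is about 9%, against 1 − 0.95^2 = 9.75%.

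**The case against.** The strongest reply is that this is a loosely worded secondary analysis. The sentence before the regression concerns symptom incidence, the one after it promises ORs, and every symptom has a yes/no item. Read together, they point to logistic regression. That reply largely stands. A reader might infer that a linear model is planned and the promised ORs are impossible, but the SAP never says linear. The remaining fault is that neither model nor outcome is named.

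A reader might also infer that every airway and anesthesia variable will be entered. The documents do not support that: the Description lists data to collect, and the SAP leaves the model's contents open. The figures for large models show what could happen, and do not describe the plan.

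Third, the clip question is answered by the t-test and chi-square test, and randomisation makes these unadjusted comparisons valid. This stands. Omitting a randomised arm also does not exaggerate covariate ORs; if anything it attenuates them slightly. What is lost is an adjusted estimate of the clip effect and any precision that adjustment would bring.

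Finally, a baseline yes/no item could be sparse, because severe cases of three symptoms are excluded. That is a fair caution about fitting the model, and a penalised fit addresses it. It is not a reason to leave the baseline value out of the plan.

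**Conclusion.** The point holds in a limited form. The SAP promises ORs from a regression whose type and outcome are unstated and whose stated predictors include neither arm nor the baseline symptom. No adjusted clip effect is therefore planned, although the data for one are collected. This rests on the text alone and needs no simulation. The precision forgone cannot be calculated, because the documents do not say how strongly baseline symptoms predict later ones.

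The risk to the covariate ORs is conditional. On the OR scale the average overstatement is roughly 12% to 57% across the 12-covariate and 17-term settings, and about 2% to 7% in the short ones. All of these figures depend on assumed incidences and covariate counts. A reader might conclude that the reported ORs would necessarily be undefined or exaggerated. The documents do not support that, since a short logistic model of the yes/no item would give usable ORs and nothing in the SAP rules one out.

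**What to change.** Replace the two modelling sentences in the Statistical Analysis Plan with a specification that:

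- names logistic regression for the yes/no symptom, or ordinal logistic regression for the 0-10 score, at one named symptom and time point;
- always includes treatment arm and the baseline value of that symptom, and reports the adjusted clip OR with its 95% CI beside the unadjusted comparisons;
- adds only a few pre-specified covariates known before the clip is placed, for example sex and tube size. Procedure time does not qualify, because it is known only afterwards;
- excludes variables that exist only in the clip arm (clip duration, placement time) and those arising after clip placement (such as trauma at extubation);
- uses Firth penalisation if events or baseline symptoms are sparse;
- labels the covariate ORs exploratory.

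Arm, baseline, sex and tube size as a linear term make 4 terms. At incidences of 10%, 20%, 40% and 50% that is 10/4 = 2.5, 20/4 = 5, 40/4 = 10 and 50/4 = 12.5 events per term, so the penalised fit matters mainly at the lower rates. This exact model was not simulated; the 3-term results are the nearest guide.

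The change needs SAP wording and no new data. The cost is that fewer predictors are examined. Enrollment is already shown as actual, so the change should be dated and made before outcomes are analysed by arm, or else reported as post hoc.
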